The interactions that occur between viral surface proteins and host cell receptors are the way for viral transmissibility¹². SARS-CoV-2 expresses the surface glycoprotein S1, which contains a receptor binding domain (RBD) that interacts with the angiotensin-converting enzyme 2 (ACE2), enabling the onset of infection.¹³ Previous studies demonstrated that heparin and its analogues are able to bind to the SARS-CoV-2 spike protein and block SARS-CoV-2 infection using therapeutic relevant concentrations. Such inhibition is likely to be caused by overlapping heparin / HS binding sites on S1 RBD restricting binding with the angiotensin-converting enzyme 2.¹⁴

We have developed a method to enrich commercially available unfractionated heparin through simple filtration. Unfractionated heparin, containing chains of molecular weight between ~5,000 Da and ~30,000 Da,¹⁵ is filtered (Amicon-10 kDa® centrifuge - MilliporeTM) to obtain an enriched heparin preparation that possesses higher amounts of chains of molecular weight greater than 10,000 Da.

This enriched heparin showed antiviral action *in vitro* (data not shown), using standardized cell-based assays in the VERO cells infected with a clinical isolate SARS-CoV-2/SP02/human/2020/BRA (GenBank access n° MT126808.1). Upon heparin treatment, there was a variable decrease in viral load up to 100% with no observed cytotoxicity in the tested doses (62.5µg/mL to 250µg/mL). Together with widespread evidence that heparin molecular weight affects its anti-SARS-CoV-2 infectivity, we envisage that this enriched heparin preparation can be more effective in viral inhibition.

Inhaled Heparin

The mechanism of nebulized heparin has been tested in several clinical studies in the last two decades, mainly for the treatment of acute airway inflammation caused by smoke inhalation and severe acute respiratory diseases.¹⁶ As it is a systemic anticoagulant, the administration of heparin by inhalation presents an initial concern regarding the risk of bleeding during treatment. However, it is known that the systemic absorption of heparin by this route is minimal.

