A study carried out by Bendstrup, et al (2002),¹⁷ evaluated the effects of the inhibition of systemic coagulation through nebulized unfractionated heparin at doses up to 64 mg and identified that there is a dose-dependent effect for factor Xa inactivation, inducing minimal changes in aPTT, and it is safe for clinical or research purposes, without increasing the risk of bleeding.¹⁸

Phelps, et al (2020),¹⁹ carried out a systematic review on the use of UFH inhalation for the treatment of inhalation injury caused by heat in burn patients and concluded that nebulized heparin did not demonstrate an increase in the risk of bleeding rates and decreased the duration of mechanical ventilation.

For COVID-19, the heparin anti-viral effect is expected to be related to the fact that heparin blocks viral interaction with host receptors thereby inhibiting virus interaction with the cell and, consequently, viral invasion.^{20, 21} To this moment, some studies indicate that treatment with systemic heparin reduced hospital mortality in patients with COVID-19²² and a previous study that strongly supported the clinical investigation of heparin as a potential treatment for patients with COVID-19,^{23, 24} justifies further investigation to prove these clinical effects.

Objectives

Primary objectives assessment

Safety: related to the use of nebulized enriched heparin by patients with SARS-CoV-2 through the assessment of hemorrhagic events of any nature, alteration of the coagulation testing, like prolonged activated partial thromboplastin time (aPTT), indicated by an increase in aPTT>1.5, and heparin-induced thrombocytopenia; Efficacy: related to the proposed treatment, through analysis of the SARS-CoV-2 viral load of the participants treated by the sequential assessment of reverse transcription-polymerase chain reaction (RT-PCR) in the nasal swab.

Secondary objectives assessment

Safety measured by respiratory, clinical, laboratorial and tomographic findings as follows, in number of patients, and hospitalization days:

Supplemental oxygen therapy needed;

Mechanical pulmonary ventilation needed;

Renal failure development;

Development of major cardiovascular events such as pulmonary embolism and acute myocardial infarction;

Demand for intensive care unit (ICU) treatment;

Secondary pulmonary bacterial infections (bacterial pneumonia);

Deep vein thrombosis (DVT) through Doppler ultrasonography assessment;

Pancreatitis characterized by increase in amylase >200 U/L;

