The reasons for discontinuing treatment will be properly documented by the research team and, in case the study is closed, the researchers will ensure the continuity of the medical and hospital assistance to the participant.

If COVID-19 is not confirmed by RT-PCR within 72 hours of the inclusion, the patient will be withdrawn from the study.

Randomization and study arms

Participants will be divided in two groups and randomized 1:1. In this way, they will receive a sequential inclusion number from an electronically drawn number table and will receive the treatment according to the allocation in one of the groups:

Group 1 - Control: Nebulization with 10mL of 0.9% saline solution, administered every 4 hours for 7 days, except the nebulization that would be administered between 12pm and 6 am (5 inhalations per day).

Group 2 - Experimental: Nebulization with enriched heparin (250 μ g/mL diluted in 10mL of 0.9% saline solution), administered every 4 hours, for 7 days, except the nebulization that would be administered between 12 pm and 6 am (5 inhalations per day).

The randomization list will be prepared by an independent statistician, using Stat Trek, a program to construct random number tables, available at <http://stattrek.com/Tables/Random.aspx>. Fifty positions will be drawn in a random and consecutive manner. The envelope containing the randomization will be kept in possession of an independent professional (pharmacist), so that the members of the study team will not know the order of allocation.

Blinding

The clinical trial will be triple-blind. Participants, researchers, the data and statistical analysis team will not have access to the allocation numbers. A pharmacist will produce the heparin and the placebo and will assign a researcher of the team to distribute the product to each participant, according to the randomization list. In addition, presentation of the preparation to the control and experimental group will be identical, since enriched heparin is colorless and odorless to the human eye and nose, as well as the saline solution. The blinding code will not be broken until all research participants have completed the study and the database is closed, that is, it will not undergo further changes. In an emergency, and if necessary, members of the data and security monitoring committee can request a blinding break, only for the participant at risk.

Sample size, recruiting and statistical analysis

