The total recruitment size will be 50 participants, aiming at 40 patients followed during the study period. The sample was estimated considering the number of patients diagnosed as COVID-19 at the São Paulo State University (UNESP) Clinical Hospital that met the study's eligibility criteria.

The sample calculation of 40 patients took into account two independent study arms, with an estimated proportion in the viral load reduction rate of 30% for group 1, that will receive placebo, and 75% for group 2 that will be treated with enriched nebulized heparin as proposed in this study, considering 80% test power and a 5% significance level for a bilateral test.

Categorical variables will be evaluated with Fisher's exact test, continuous variables will be compared with non-parametric methods such as Mann-Whitney test or U test, paired comparisons will be evaluated with the Wilcoxon test, multivariate analyzes will be evaluated with regression Cox analysis and long-term clinical analyzes will be compiled on Kaplan-Meir curves.

Interventions and inpatient schedule

Intervention	Day 0	Day 1	Day 2	Day 3	Day 4	Day 5	Day 6	Day 7	Day 8
Informed consent form	X								
Medical visit, patient story and physical examination	X	X	X	X	X	X	X	X	X
Vital signs assessment	X	X	X	X	X	X	X	X	X
Medications in use	X	X	X	X	X	X	X	X	X
Inclusion and exclusion criteria	X								
COVID-19 viral load in RT-qPCR	X		X			X		X	X
Complete blood count, D-dimer, aPTT, urea, creatinine, glucose, reactive protein C, blood gas and amylase	X		X			X		X	X
Computed thoracic tomography	X								X
HMWH or placebo administration		X	X	X	X	X	X	X	X
Adverse events	X	X	X	X	X	X	X	X	X
Discontinuation criteria	X	X	X	X	X	X	X	X	

Table 1. Schedule for assessments and intervention. The participants will be followed up and evaluated on days 0, 1, 2, 3, 4, 5, 6, 7 and 8 days after randomization.

The closure assessment will be carried out on day 8. Extra data can be collected if the patient's clinical condition changes. Randomization will be performed in up to 24 hours after admission. After the end of the study, the participant will be referred and accompanied at the COVID-19 outpatient clinic São Paulo State University (UNESP) Clinical Hospital.

Adverse events

Adverse effects related to the nebulized use of heparins will be tracked and analyzed according to the Common Terminology Criteria for Adverse Events (CTC-AE 5.0),²⁵ and will be graded from 1 to 5, accordingly to the severity of the event.

Grade	Description

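### On-treatment viral-load swabs have no timing rule relative to nebulisation and no described assay control, so residual heparin in the specimen is not excluded as a cause of lower measured viral load

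*Combined protocol and SAP*

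**What the plan says.** The primary objectives define efficacy as viral load from "sequential assessment of reverse transcription-polymerase chain reaction (RT-PCR) in the nasal swab". In Table 1 the row "COVID-19 viral load in RT-qPCR" is marked on Days 0, 2, 5, 7 and 8. The row "HMWH or placebo administration" is marked on Days 1 to 8.

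Under Randomization and study arms, the control group receives "Nebulization with 10mL of 0.9% saline solution, administered every 4 hours for 7 days". The experimental group receives heparin "diluted in 10mL of 0.9% saline solution), administered every 4 hours, for 7 days". Both follow the same pattern, "except the nebulization that would be administered between 12pm and 6 am (5 inhalations per day").

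The Rationale reports earlier work in which "heparin and its analogues are able to bind to the SARS-CoV-2 spike protein". Under Dosage and administration, the dose is chosen to reach, after dilution in lung fluid, the concentrations tested in vitro (62.5 to 250 μg/mL).

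The laboratory form (Figure 3) has a date, a positive/negative result and a quantitative viral load. It has no collection time, no time since last dose and no control result. Time since last dose is a field on the adverse events form only. The text describes no internal control, recovery check or clean-up step for the RT-qPCR.

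**The concern.** The specimen comes from the upper airway of patients who are inhaling study product, and only one arm's product contains heparin. If heparin carried into the swab lowered RNA recovery or delayed amplification, viral load would read low in that arm alone. That reading would look the same as reduced replication, which is the effect the trial sets out to detect.

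Blinding does not help, because the difference would sit in the specimen and not in anyone's handling of it. The Day 0 swab does not help either: it precedes dosing, so a change from baseline would carry the whole artefact. Without swab times, last-dose times or control results, no later analysis could separate the two explanations.

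**Working it through.** **1. Which swabs fall on dosing days.** Post-baseline swabs are on Days 2, 5, 7 and 8. With dosing on Days 1–8 (Table 1), all four are on dosing days. With 7 days of dosing from Day 1 (arm text), Days 2, 5 and 7 are, and the Day 8 closing swab is not. Three of the four are exposed on either reading.

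**2. Whether a pre-dose swab fits the schedule.** Dosing every 4 hours gives 24/4 = 6 slots a day, and five are used. Five doses span 4 × 4 = 16 hours, which leaves 24 − 16 = 8 hours overnight. (This reads the stated 12 pm as midnight; noon to 6 am would leave only 6 hours for five doses.)

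**3. The plan's sample size.** Inputs from the sample-size section: 30% vs 75%, 80% power, two-sided 5%, 1:1.

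n per arm = [1.96·√(2·0.525·0.475) + 0.8416·√(0.30·0.70 + 0.75·0.25)]² / 0.45² = (1.384 + 0.531)² / 0.2025 ≈ 18.1, so 19 per arm and 38 in total. This agrees with the stated 40 to within 2 patients, and 40/(1 − 0.20) = 50 recruited. The calculations below use 20 per arm.

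**4. Size of the risk, continuous viral load.** Everything here except the 20 per arm and the Mann-Whitney test is an assumption: no true effect; normal log10 viral load (or change) at one on-treatment visit; between-patient SD 1.0, 1.5 or 2.0; artefactual delay of 1, 2 or 3 cycles, each log10(2) = 0.30, so 0.30, 0.60 or 0.90 log10; and a stated share of heparin swabs affected. The entries are the percentage of 20,000 simulated trials with two-sided p ≤ 0.05 favouring heparin.

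| Share of heparin swabs affected | SD | 1 cycle | 2 cycles | 3 cycles |
|---|---|---|---|---|
| All | 1.0 | 14.5 | 43.9 | 77.2 |
| All | 1.5 | 8.5 | 22.7 | 43.5 |
| All | 2.0 | 6.5 | 14.8 | 26.8 |
| Half | 1.0 | 6.3 | 14.1 | 24.7 |
| Half | 1.5 | 4.8 | 8.3 | 13.8 |
| Half | 2.0 | 4.0 | 6.2 | 10.0 |
| Quarter | 1.0 | 4.0 | 6.1 | 9.3 |
| Quarter | 1.5 | 3.5 | 5.0 | 6.3 |
| Quarter | 2.0 | 3.2 | 4.2 | 5.1 |

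With no delay the figure is 2.3–2.6%. Simulation error is at most √(0.25/20,000) ≈ 0.35 percentage points. Smaller simulations put the lower end for all swabs at about 6% and for half between 3 and 4%.

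**5. Size of the risk, binary reduction.** The sample-size calculation uses a proportion, and the plan assigns Fisher's exact test to categorical variables. Assume a true reduction rate of 30% in both arms, with a fraction f of heparin non-reducers misread as reduced. The heparin arm's apparent rate is then 0.30 + 0.70f. Exact probabilities of a significant result favouring heparin at 20 per arm:

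| f | Apparent rate | Probability |
|---|---|---|
| 0 | 30% | 1.2% |
| 0.1 | 37% | 3.8% |
| 0.2 | 44% | 9.0% |
| 0.3 | 51% | 17.8% |
| 0.4 | 58% | 30.4% |
| 0.5 | 65% | 46.8% |

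**The case against.** The strongest objection is that the harmful link is not in the documents. They say that heparin binds the spike protein and blocks infection, which is the hypothesised treatment effect. They do not say that binding lowers the RNA recovered from a swab, or that heparin disturbs this assay. The delivery interface (mask or mouthpiece) is not stated, so the amount of drug reaching the nose is unknown. A reader might infer that the endpoint is already biased towards heparin; the documents do not support that. This part of the objection stands, and the point is limited to a risk that is not excluded.

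A reader might also infer that 10 mL of liquid washes virus away in one arm only. Both arms inhale the same saline volume on the same schedule, so vehicle wash-off is shared. Only a heparin-specific effect could differ.

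The upper figures require every heparin swab to be affected. With swab timing left free, only some swabs would closely follow a dose, so the rows for half and a quarter matter as much.

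A laboratory manual, not supplied, may already contain an amplification control or a collection time. Nor do the documents show that an overnight gap clears heparin, so a timing rule alone is not proven protection. Both objections are fair. They are reasons to state the control and report it by arm, not reasons to leave the plan silent.

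Finally, the main stated intention of this phase I/II trial is safety. Viral load is still its primary efficacy measure and the basis of its sample-size calculation.

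**Conclusion.** The gap is real and worth closing. On Days 2, 5 and 7, and on Day 8 if dosing runs to Day 8, the primary efficacy specimen is taken while one arm inhales heparin. Nothing in the plan would prevent, detect or adjust for drug in the specimen.

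The size is conditional. Under the assumptions in the working, the chance of a false significant benefit is about 6–77%, 4–25% or 3–9% when all, half or a quarter of heparin swabs are affected, against a nominal 2.5%. If heparin does not reach the swab or does not affect the assay, there is no bias. The direction also rests on the assumption that any interference lowers the reading.

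The rule that withdraws patients not confirmed by RT-PCR within 72 hours touches this point only narrowly. The window can include the on-treatment Day 2 swab, but Table 1 already has a Day 0 test before dosing, and some patients enter already confirmed. A reader might infer that confirmation should rest on the Day 0 swab alone. That does not follow: it would withdraw patients whom a repeat test within 72 hours would have confirmed.

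**What to change.** - State under Table 1 that every on-treatment viral-load swab is taken before the first nebulisation of that day.
- Add two fields to the laboratory form: swab collection time and time of last nebulisation. The adverse events form already collects time since last dose, so this is feasible.
- Name the internal or human-gene amplification control used in the RT-qPCR, and report its Ct by arm at each visit.
- Reconcile the 7-day arm text with the Day 1–8 row of Table 1, so that it is clear whether the Day 8 swab is on or off treatment.
- Leave the 72-hour confirmation open to repeat tests.

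A blinded spike-recovery check, adding study-strength heparin to a few positive samples, is optional; it would test the assay assumption directly at the price of some laboratory work.

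The cost is a fixed morning swab time, two form fields and one extra tabulation. The number of swabs, the visits, the dosing and the sample size do not change.
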